13.0 Recruitment Methods

13.1 Participants will be recruited from the general population of Tallahassee, FL and surrounding rural areas within reasonable commuting distances. Participants will be recruited via public service announcements, social media, and flyers posted on campus, in health clinics and fitness centers, and in employment development centers.

13.2 The source of subjects will be from active local members of the community who meet the inclusion criteria.

13.3 The PI will, in the recruitment materials, include general inclusion and exclusion criteria, as well as the investigators' contact information. Individuals interested in participating in the study will contact an investigator (via telephone or email). Volunteers interested in participating will then be scheduled to meet with the investigator to have the study and what is expected of them explained in detail and have their questions answered. Prior to the initiation of any tests or measurements, an informed consent to participate in the study will be obtained in writing by the investigator.

13.4 Participants will be recruited via public service announcements, social media, and flyers posted on campus, in health clinics and fitness centers, and in employment development centers. (Copy attached)

13.5 Upon completion of the study, participants will be compensated for their participation with a \$100 VISA gift card, an amount comparable to past studies similar in nature and extent. Complete participation is required to earn the gift card.

14.0 Withdrawal of Subjects

- 14.1* Subjects will be withdrawn from the research without their consent if they do not comply with prescribed bed and wake times for the entirety of either intervention.
- 14.2* Upon discovering the adherence problem, participants will be contacted via telephone or face-to-face and politely told they are disqualified from continuing the study due to adherence.
- 14.3* If participants withdraw of their own volition or are withdrawn by the PI, the research team will notify them via phone call or word of mouth in person. All data collected up until the point of withdrawal may be used at the PI's discretion for the results.

15.0 Risks to Subjects

- 15.1* The reasonably foreseeable risks, discomforts, hazards, or inconveniences to the subjects related the subjects' participation in the research include:
- Physical discomfort from intravenous blood draws: Yet, blood will be taken by researchers previously trained and experienced in phlebotomy, following the biological safety procedures in place for a level two laboratory.
 - Possible inconvenience of missing work if they adhere to a traditional work schedule: Yet we can schedule experimental visits early in the morning before traditional hours to accommodate these needs.
 - Possible risk of adverse cardiac event or injury during maximal treadmill testing: Yet, the established risk of event is 6 in 10,000 and the tests will be performed by researchers previously trained and extensively experienced (10+ years) in administering the test.
- 15.2* Unforeseeable risks may include the expression of a genetic condition that was not "caught" by the screening process. Yet, efforts will be made to ask the subject if there is any reason why they think it is to their detriment if they participate in this protocol.
- 15.3* N/A. Pregnant women will not be included in this study
- 15.4* Blood will be collected following biological safety procedures in place for a level 2 laboratory. However, accidental needle sticks or exposure to potential pathogens via blood is always a possibility. In such a case, wounds will be cleaned and bandaged appropriately and incidents will be reported.

16.0 Potential Benefits to Subjects

- 16.1* The potential benefits that individual subjects may experience from taking part in the research include gathering important metrics for

their health and fitness. Depending on the outcome of the study, participants may also discover a viable health-promoting practice.

16.2 N/A

17.0 Data Management and Confidentiality

17.1

Sample Size Estimation

Sample size requirements were determined via a priori power analyses using G*Power software (Ver. 3.1.9.4; Heinrich-Heine-Universität Düsseldorf, Düsseldorf, Germany) to ensure sufficient statistical power. To inform the expected effect size, we referenced Sunbul, et al. (49) who reported significantly higher wave velocity (PWV) values (5.33 ± 0.46 m/s) following one night of total sleep deprivation compared to one night of normal sleep (5.15 ± 0.26 m/s; $p=0.001$) in young, healthy males and females. Acknowledging that this will consist of an acute partial sleep deprivation intervention, a Cohen's f value of 0.24 was used in conjunction with an α level of 0.05, power of 0.80, with 2 groups (crossover design; 4 measures each), and a conservative correlation among repeated measured of 0.5. This resulted in a sample size estimate of 24 participants. The planned sample size was then increased based on the differences between the current study, the previous work, and the assessment of several secondary outcomes, as well as to account for expected attrition (~20%). Therefore, 30 participants will be recruited to maximize statistical power and account for expected attrition.

Statistics

Data will be presented as means \pm SD if normally distributed and assessed for normality via a Shapiro-Wilk Test. Assuming normality, all variables will undergo null-hypothesis testing with the α level set to 0.05. In the case that normality is violated, the appropriate non-parametric alternatives will be utilized. Analyses will be conducted using SPSS version 29.0 (SPSS, Inc., Chicago, IL).

Analysis of Variance: Central hemodynamic and arterial stiffness variables will be interpreted using a mixed-model (i.e., within-between) repeated measures analysis of variance (RMANOVA) to identify interactions between multiple groups and conditions. Specifically, to test the hypothesis that individuals with higher CRF would demonstrate a blunted arterial stiffness response (i.e., maintained pulse transit times) to the acute partial sleep deprivation intervention, cf-PWV will be assessed following 4 consecutive nights of both normal sleep and restricted sleep and compared between the two groups. Likewise, all secondary variables will be assessed at pre-specified time points using a within-between interaction RMANOVA to test the hypotheses that individuals with higher CRF would demonstrate a blunted effect of partial sleep deprivation on markers of physical and cognitive performance (i.e., maintained RSI and PVT, respectively) as well as on markers of overall health (i.e., maintained cardio-autonomic function parameters, pro- and anti-inflammatory serum cytokine levels, and mood states).

In the case that sphericity is violated, a Greenhouse-Geisser correction will be performed. In the case of significance, a post hoc one-way ANOVA with Bonferroni tests will be used to identify significant differences. Effect sizes (ES) will be calculated by standardizing mean differences to the standard deviations (SD) of the placebo condition. Effect sizes will be qualified as follows: small $d = 0.2$, moderate $d = 0.5$, and large $d \geq 0.8$ (50).

17.2 The data will be kept secure through several routes. First, only the CITI certified research team will be allowed to be involved in the data collection process. Further, after acute bouts of data collection occur, all data will be collected together by the PI. If the data is physical, it will be kept in a locked drawer, behind a locked laboratory door. If the data is electronic, it will be kept on a password secured computer that only the PI may gain access. All human data will be coded, such that without the code it becomes unidentifiable.

17.3 Quality control of collected data will be ensured by controlling as many external variables as is reasonable. Further, biological measures (primary outcomes) will be measured in duplicate with the average of each measure used in the final assessment.

17.4 Describe how data or specimens will be handled study-wide:

- The information will be included in the data or associated with the specimens will be coded and unidentifiable without the code. The code will be kept in physical copy behind two locked doors and a third locked drawer, or in electronic copies in a password protected file.
- Specimens will be kept in closed containers within the ISSM freezer (-80° C) behind two locked doors for batch analysis. After the analysis of the data, specimens will be maintained for 3 years. Data will be kept on password protected FSU computers or in physical copies behind locked drawers and doors in the PI's office.
- Specimens will be stored for 3 years after initial analysis.
- The verified research team are the only people who will have access to the data or specimens.
- The PI will be responsible for receipt or transmission of the data or specimens until graduation. After such event, the co-investigator, [name], will be responsible for receipt or transmission of data or specimens.

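### The 80% power claim uses the whole total-deprivation condition effect (f = 0.24), but the hypothesis is a fit-versus-unfit difference in response; if the unfit respond by 0.18 m/s and the fit not at all, power is about 20–25%.

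*Combined protocol and SAP*

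**What the plan says.** Section 17.1 (Sample Size Estimation) takes its effect size from a published study of pulse wave velocity, giving "values (5.33 ± 0.46 m/s) following one night of total sleep deprivation compared to one night of normal sleep"; the comparison value was 5.15 m/s with an SD of 0.26. The sentence that introduces the effect size opens by noting the milder exposure planned here: "Acknowledging that this will consist of an acute partial sleep deprivation intervention". The settings of the power analysis then follow, in which an "f value of 0.24 was used in conjunction with an α level of 0.05, power of 0.80". The layout entered is two groups, four measures per person and a correlation of 0.5 that the plan describes as conservative. The section reports the output in one line: "This resulted in a sample size estimate of 24 participants". The number is then raised to 30 for differences from the earlier work, several secondary outcomes and about 20% attrition.

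The hypothesis is of another kind. Section 2.0 (Aim 1) expects a smaller rise in blood pressure and arterial stiffness in the high-fitness group. Section 17.1 (Analysis of Variance) tests whether "individuals with higher CRF would demonstrate a blunted arterial stiffness response", using a within-between repeated measures ANOVA that compares cf-PWV after normal and restricted sleep between the two groups. No section states how far the response is expected to differ between fit and unfit participants.

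**The concern.** The source contrast, as the plan reports it, compares two sleep conditions in one sample: "following one night of total sleep deprivation compared to one night of normal sleep". It says how much pulse wave velocity rises without sleep. It does not say how much that rise differs by fitness, which is what the primary test estimates. A difference between two responses is usually smaller than the response itself and is estimated less precisely. Entering the condition effect as the interaction effect therefore attaches 80% power to a question it was not calculated for.

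Two things are at stake. The plan assigns the primary analysis a property that it may lack by a wide margin. And a non-significant interaction could be presented as an adequately powered negative finding on whether fitness protects.

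**Working it through.** **Inputs.** From Section 17.1: means 5.33 and 5.15 m/s, SDs 0.46 and 0.26, alpha 0.05, power 0.80, f = 0.24, 2 groups, 4 measures, r = 0.5, N = 24. For completers: Section 17.1 recruits 30 with about 20% attrition, so 30 × 0.8 = 24; Section 12.2 recruits up to 36 to finish with 30. Equal groups are assumed.

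**Formula.** Interaction test in a repeated measures ANOVA with k groups and m measures: λ = f² × N × m / (1 − r), with df (k − 1)(m − 1) and (N − k)(m − 1). Power comes from the noncentral F.

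**Step 1: the plan's figure.** With f = 0.24, k = 2, m = 4, r = 0.5 and N = 24, λ = 0.0576 × 24 × 4 / 0.5 = 11.06 on 3 and 66 df. Power is 78.0%; N = 26 gives 81.7%. The stated 24 is reproduced to within two participants.

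**Step 2: where 0.24 comes from.** Pooled SD = √((0.46² + 0.26²)/2) = 0.374. d = 0.18/0.374 = 0.482. f = d/2 = 0.241. This is the source effect with nothing taken off for partial deprivation.

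**Step 3: f as an interaction.** If the two groups' responses differ by D, each cell of the 2 × 2 table departs from additivity by ±D/4, so f = D/(4 × 0.374).
- f = 0.24 requires D = 4 × 0.24 × 0.374 = 0.36 m/s, twice 0.18.
- D = 0.18 (unfit 0.18, fit 0) gives f = 0.045/0.374 = 0.12.

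**Step 4: power for the two-condition contrast** (m = 2, r = 0.5, 1 and N − 2 df). For D = 0.18, λ = 0.1204² × 24 × 2 / 0.5 = 1.39, or 1.74 at N = 30.

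| Unfit response, fit response (m/s) | D | Power, N = 24 | Power, N = 30 |
|---|---|---|---|
| 0.18, 0.09 | 0.09 | 9% | 10% |
| 0.18, 0 | 0.18 | 20% | 25% |
| 0.27, 0 | 0.27 | 39% | 48% |
| 0.36, 0 | 0.36 | 61% | 72% |

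For D = 0.18, 80% power needs about 138 participants.

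**Step 5: sensitivity for D = 0.18.**
- Correlation (range assumed): r = 0.3 gives 16% and 19% (N = 24 and 30); r = 0.7 gives 31% and 37–38%; r = 0.8 gives 43% and 52%; r = 0.9 gives 71% and 81%.
- Unequal SDs: keeping 0.46 and 0.26, the SD of the change at r = 0.5 is √(0.46² + 0.26² − 2 × 0.5 × 0.46 × 0.26) = 0.40, and a two-sided t test on changes has 18% and 22% power.
- Four measures: 24% and 30% if the effect is present at both restricted-sleep time points; 19% and 23% if only at the post-test.

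**Step 6: detectable difference at 80% power** (m = 2, r = 0.5). The required f is 0.299 at N = 24 and 0.265 at N = 30. Then D = 4 × f × 0.374 = 0.45 m/s and 0.40 m/s, which is 2.5 and 2.2 times the reference effect.

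**The case against.** Four points deserve weight.

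- *The scenario is not a ceiling.* A reader might infer that 20–25% is the best the trial can do, or that it could not detect complete protection. The documents do not support that. The figure fixes the unfit response at 0.18 m/s. The source sample is described only as young and healthy, with no split by fitness, after one night; this trial compares fitness extremes after four nights. If 0.18 were the average of an unfit response of 0.36 and a fit response of zero, power would be 61–72%. A smaller response to partial restriction is just as possible and would lower it. The documents cannot choose, so the figure must be stated conditionally.
- *The correlation may exceed 0.5.* The plan calls 0.5 conservative, and Section 17.3 averages duplicate measurements. This stands, and the range over r belongs in the statement. Only near r = 0.9 with 30 completers does power reach 80%, and that relies on equal SDs: with the cited unequal SDs it is 47% there.
- *The software result is right.* Largely true (Step 1), so this is not a miscalculation; the effect size belongs to a different hypothesis. Nor does the plan say that a discount was made. It acknowledges partial deprivation and says the sample was enlarged partly for differences from the earlier work. But 24/0.8 = 30, so attrition alone uses up the increase.
- *The plan has four measures, not two.* Section 17.1 (Analysis of Variance) defines the cf-PWV contrast by the two conditions. Section 6.2 describes a repeat three days later, while its account of the recovery visits lists only blood work and jump testing. With four measures the range is 19–30%, so the conclusion is unchanged.

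**Conclusion.** The concern holds in conditional form. The 80% power in Section 17.1 is calculated with the undiscounted condition effect of total deprivation and is not supported for the group-by-condition hypothesis. Read as an interaction effect, f = 0.24 presupposes a 0.36 m/s difference in response that the plan neither states nor justifies, and the two-condition test would still fall short of 80% with 24 or 30 completers.

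The 20–25% figure rests on an unfit response equal to the reference, no response in the fit, a pooled SD of 0.374 carried over from the cited study, r = 0.5 and equal groups. Power rises with a larger unfit response or a higher correlation, and falls if partial restriction has less effect. The documents also contain no rule that a null interaction will be read as absence of protection; the point is that the stated power would lend such a reading unearned support.

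**What to change.** Keep the sample size and design. In Section 17.1:

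1. Remove the claim that 24 (or 30) participants give 80% power for the primary hypothesis, and align Section 25.0, which says the power analysis required 30.
2. Reconcile the number of completers: about 24 follows from Section 17.1, 30 from Section 12.2. State also whether cf-PWV is measured twice or four times.
3. Insert, with the inputs labelled as assumptions: *Assuming an SD of 0.37 m/s, a within-person correlation of 0.5 and equal groups, the group-by-condition test has 80% power for a difference in cf-PWV response of 0.45 m/s with 24 completers or 0.40 m/s with 30. If restriction raises cf-PWV by 0.18 m/s in the unfit group and not at all in the fit group, power is about 20% or 25%.* Add the range over the correlation and the unfit response.
4. Name the difference in response between groups, with its 95% CI, as the primary result, so that a non-significant interaction is not presented as an 80%-powered negative.

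The cost is rewording and a less favourable stated power. No participants, visits or procedures are added.

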Experimental Visits: Following the first sleep intervention period, participants will come in for the first of four data collection visits (i.e., Post-Test 1). Data collection visits will begin of the completion of the Pittsburgh Sleep Quality Index (PSQI) and Profile of Mood States (POMS) questionnaire to characterize sleep quality and psychological mood states, respectively. Next, central arterial pulse wave form analysis and pulse transit time (carotid-femoral PWV [cf-PWV]; via applanation tonometry) will be assessed using a SphygmoCor XCEL device (AtCor Medical, New South Wales, Australia), followed by a standard venipuncture procedure to allow for inflammatory marker characterization, total blood cell counting, as well as blood lipid and glucose profiling to account for known hemodynamic confounders (26). The venipuncture procedure will be performed by the primary investigator (certified phlebotomist trained; 5+ years of experience) following the attached standard operating procedure for venipuncture and will entail the collection of 10-30 mL of blood, as is typical of a standard blood venipuncture procedure. If the primary investigator is unavailable to perform the procedure or is unable to do so, the Clinical Research and Trials Unit will be utilized. Lastly, participants will perform a short countermovement jump (CMJ) test to quantify their reactive strength index (RSI).

Participants will then undergo a 7-day washout/ post-intervention observation period, in which they will continue to track and log their sleep and perform daily PVT to allow for recovery evaluation in those metrics, prior to crossing over to the other sleep intervention. During the washout period, participants will also return to the lab to repeat the blood work and CMJ testing to allow for recovery assessment in those values (i.e., immediate post-intervention vs 3-day post-intervention values; Recovery 1). Following completion of the washout/observation period, participants will be assigned to the other sleep intervention in a crossover fashion and complete the second 4-day intervention before returning for another data collection visit (i.e., Post Test 2) identical to Post Test 1. They will then enter another 7-day post-intervention observation period and performing a second recovery data collection visit (i.e., Recovery 2). Data collection visits will occur at the same

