approximate time of day for each individual to account for diurnal patterns in the data collected. In total, the protocol will last approximately 5 weeks and consist of 5 visits.

Central Hemodynamic Assessment: Participants will be assessed for central arterial pulse wave form and cf-PWV following both sleep interventions with re-analysis occurring 3 days later to quantify the response to, and recovery from, the two sleep interventions between the two groups. The central hemodynamic (i.e., central blood pressure, augmentation index [absolute and relative to a heart rate of 75 beats per minute], mean arterial pressure, and pulse pressure) and arterial stiffness (i.e., cf-PWV) variables of interest will be collected and analyzed following methods identical to those utilized by Grosicki, et al. (34).

Health and Well-Being Assessment: Both metrics of sleep quality and cardio-autonomic function (i.e., resting heart rate, heart rate variability, and a proprietary, WHOOP-generated recovery score) will be collected via the WHOOP devices. The wearing of the device throughout the entirety of the project timeline will allow for the quantification of these measures in response to, and recovery from, the two sleep interventions, which will be compared between the two groups. Further, data from the devices will be analyzed following protocols set forth by Greenwalt, et al. (44). Using blood samples collected during the venipuncture protocols performed at the four data collection visits, sleep intervention response and recovery levels of circulating plasma concentrations of pro- (CRP, IL-6, IL-1 β , and TNF- α) and anti-inflammatory (IL-10) cytokines will be assessed using protocols similar to that outlined by Smith, et al. (45). Additionally, portions of the blood samples will undergo hematologic analysis to characterize shifts in the composition of immune cells through methods similar to those of Schluter et al. (46). Finally, POMS data will be used to evaluate intervention-associated shifts in psychological mood states between the two groups following the methodology of Shacham (47).

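### The sample size is powered for a four-measure interaction, but the stated primary cf-PWV test uses two measures; on the plan's own inputs that test has 61% power at 24 participants and 72% at 30, not 80%

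*Combined protocol and SAP*

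**What the plan says.** Section 17.1, Sample Size Estimation, states that "a Cohen's f value of 0.24 was used in conjunction with an α level of 0.05", followed by "power of 0.80, with 2 groups (crossover design; 4 measures each), and a conservative correlation among repeated measured of 0.5". The result is 24 participants, raised to 30 recruited to allow for about 20% attrition and for secondary outcomes. Section 12.2 differs: it allows up to 36 recruits so that 30 complete.

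The primary test is described in section 17.1, Analysis of Variance: "cf-PWV will be assessed following 4 consecutive nights of both normal sleep and restricted sleep and compared between the two groups". Aim 1 in section 2.0 describes the same two assessments, one after each four-day sleep period.

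Section 6 is inconsistent about further cf-PWV readings. Under Experimental Visits (6.2), participants in the washout "return to the lab to repeat the blood work and CMJ testing to allow for recovery assessment in those values", and section 6.1 says the same; neither lists hemodynamics at that visit. Under Central Hemodynamic Assessment (6.2), the plan is to assess "cf-PWV following both sleep interventions with re-analysis occurring 3 days later".

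**The concern.** The number of repeated measures enters the power formula directly, through both the noncentrality and the degrees of freedom. A calculation with four measures therefore does not give the power of a test on two. The figure that justifies the sample size belongs to a different test from the one that answers Aim 1.

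Two things are at stake. First, a null result for Aim 1 could be read as coming from a trial with 80% power when the power was lower. Second, the four readings behind the calculation may not exist for cf-PWV. If they do, an omnibus test over four levels combines the response to sleep restriction with the recovery from it. A significant result could then arise from recovery differences alone, which is not the Aim 1 hypothesis.

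**Working it through.** **Inputs.** From section 17.1: f = 0.24, alpha = 0.05, target power 0.80, k = 2 groups, m = 4 measures, correlation r = 0.5, stated N = 24, planned N = 30. From Aim 1 and the Analysis of Variance text: m = 2 for the primary test.

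**Formula.** For the within-between interaction in repeated-measures ANOVA, with sphericity assumed, I used the noncentral F distribution with λ = f²·N·m/(1 − r), df1 = (k − 1)(m − 1) and df2 = (N − k)(m − 1).

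**Step 1: reproduce the plan's figure (m = 4).**
- N = 24: λ = 0.0576 × 24 × 4 / 0.5 = 11.06, df 3 and 66, power 78.0%.
- N = 26: λ = 11.98, df 3 and 72, power 81.7%.

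The stated 24 is reproduced to within two participants (f = 0.25 would give 81.6% at 24). The between-group formula would need 88 participants, so the within-between interaction is the right reading of what was run.

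**Step 2: the stated primary test (m = 2), everything else unchanged.**

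| N | λ | df | Power |
|---|---|---|---|
| 24 | 5.53 | 1, 22 | 61.3% |
| 28 | 6.45 | 1, 26 | 68.6% |
| 30 | 6.91 | 1, 28 | 71.8% |
| 36 | 8.29 | 1, 34 | 79.9% |
| 38 | 8.76 | 1, 36 | 82.1% |

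With two readings and r = 0.5, this equals a two-sample t-test on change scores with a group difference of 4 × 0.24 = 0.96 SD. Simulating that t-test gives 61.3% at N = 24 and 71.8% at N = 30.

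**Step 3: which N applies.** If 30 are recruited and 20% are lost, 30 × 0.8 = 24 remain (61%). If 30 complete, as section 12.2 intends, power is 72%.

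**Step 4: where f = 0.24 comes from.** The quoted values are 5.33 (SD 0.46) and 5.15 (SD 0.26) m/s. The pooled SD is √[(0.46² + 0.26²)/2] = 0.374, so d = 0.18/0.374 = 0.48 and d/2 = 0.24. This matches a two-condition effect size, although section 17.1 does not state the derivation.

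**Step 5: sensitivity of the two-reading test.**

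| Assumption | N = 24 | N = 30 |
|---|---|---|
| f = 0.24, r = 0.3 | 48% | 57% |
| f = 0.24, r = 0.5 (plan) | 61% | 72% |
| f = 0.24, r = 0.6 | 71% | 81% |
| f = 0.24, r = 0.7 | 83% | 91% |
| f = 0.24 over four levels, effect at one reading only, r = 0.5 | 74% | 83% |

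In the last row the equivalent two-level value is f = 0.24/√0.75 = 0.277.

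**Step 6: the four-level test on the same raw effect.** If the 0.96 SD difference appears only after restricted sleep and is absent at the other three readings, f over four levels is 0.24 × √0.75 = 0.208. The 3-df test then has 64% power at N = 24 and 76% at N = 30.

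**The case against.** The best counter-argument is that four readings have a textual basis. The Central Hemodynamic Assessment paragraph describes a repeat cf-PWV three days after each intervention, and the analysis section provides for a sphericity correction and Bonferroni post hoc tests, which matter only with more than two within-person levels. But that paragraph conflicts with section 6.1 and with Experimental Visits, the sphericity and post hoc provisions may be generic or meant for secondary variables, and nothing in the plan puts recovery readings into the primary test. The specific sentence on cf-PWV names two assessments.

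A second objection is that f depends on the pattern of means over the levels, so carrying 0.24 from four levels to two is itself an assumption. This stands as a condition. The match with d/2 from a two-condition comparison favours the two-level reading without proving it.

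Third, the plan calls r = 0.5 conservative, and section 17.3 has primary biological measures taken in duplicate and averaged, which could raise the correlation if it covers cf-PWV. That also stands, but 0.5 is the only value the plan gives.

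A reader might also infer that a four-level omnibus test would dilute the Aim 1 contrast and lose power. The arithmetic does not support this: on the same raw effect the four-level test has slightly more power (64% against 61% at 24, 76% against 72% at 30). Its fault is that it tests a mixed hypothesis.

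**Conclusion.** The concern holds: the stated 80% is not the power of the stated primary test. With f = 0.24 as a two-level value, r = 0.5 and alpha = 0.05, the 1-df interaction falls about 19 points short of 80% at 24 participants and about 8 points short at 30 completers.

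It would go too far to say that the trial's power simply is 61 to 72%. That range rests on both assumptions, and with 30 completers the shortfall disappears if r is about 0.6 or if 0.24 was defined over four levels with an effect at a single reading. At 24 participants neither alternative reaches 80%. Nor is this a slip of arithmetic, since 24 is reproduced closely from the plan's own inputs. It is a mismatch between the test that was powered and the test that was specified, together with an unresolved contradiction about which readings will be taken.

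**What to change.** 1. Name the 1-df group-by-condition interaction in cf-PWV at the two immediate post-tests as the primary test.
2. Restate power for that test: 61% at 24 and 72% at 30 for f = 0.24 and r = 0.5. Say whether N means recruits or completers, bring section 17.1 into line with section 12.2 on this, state how f was derived, and show the sensitivity to r.
3. Reconcile section 6.1 and Experimental Visits with Central Hemodynamic Assessment on whether hemodynamics are measured at Recovery 1 and 2. If they are, analyse recovery as a secondary question. A group-by-condition-by-time model would serve, provided that the primary contrast at the post-tests is specified within it; recovery readings should not become levels of a single four-level primary factor.

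The cost is protocol wording. No added procedure follows from this point, but the stated power becomes less favourable.

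### On the inputs printed in Section 17.1, the stated 24 participants give about 78% power and 26 are needed for 80%: a minor slip in the sample size figure or in one reported input

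*Combined protocol and SAP*

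**What the plan says.** The only power calculation is in Section 17.1, Sample Size Estimation. It names the software, "Sample size requirements were determined via a priori power analyses using G*Power software (Ver. 3.1.9.4". Effect size, significance level and target are reported in one phrase: "a Cohen's f value of 0.24 was used in conjunction with an α level of 0.05, power of 0.80". For the design it assumes two groups, each measured four times. The within-person dependence is described as "a conservative correlation among repeated measured of 0.5". The stated outcome of the calculation is: "This resulted in a sample size estimate of 24 participants".

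The figure is then raised because the present study differs from the cited one, because there are several secondary outcomes, and because about 20% attrition is expected: "Therefore, 30 participants will be recruited to maximize statistical power and account for expected attrition".

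The sample size paragraph does not say which G*Power test was chosen. The analysis text of the same section specifies a "mixed-model (i.e., within-between) repeated measures analysis of variance (RMANOVA) to identify interactions between multiple groups and conditions".

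Two other sections use the number 30 differently. Section 12.2 allows up to 36 recruits so that 30 finish. Section 25.0 describes 30 as the size the power analysis required.

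**The concern.** An a priori calculation should return the smallest sample that reaches the target power. If the printed inputs put 24 below 80%, the reported result and the reported inputs cannot both be exact, and a reader cannot reproduce the calculation as written.

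The practical stake is limited. Section 17.1 goes from 24 to 30 recruits with about 20% attrition, and 30 × 0.8 = 24. If that step were the whole plan, the analysed sample would be 24, slightly short of the stated power. Any later recalculation that starts from 24 would also carry the discrepancy forward.

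**Working it through.** **Inputs stated in Section 17.1.** f = 0.24; alpha = 0.05; target power 0.80; k = 2 groups; m = 4 measures; correlation ρ = 0.5.

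**Inputs assumed.** The test is the within-between interaction, taken from the analysis text of Section 17.1. The effect-size option is G*Power's default. The nonsphericity epsilon is 1; smaller values lower the power.

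**Formula.** λ = f² × N × m / (1 − ρ); df1 = (k − 1)(m − 1) = 3; df2 = (N − k)(m − 1) = 3(N − 2). Power is the probability that a noncentral F with these degrees of freedom and noncentrality λ exceeds the 5% critical value.

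**The plan's figure, N = 24.** λ = 0.0576 × 24 × 4 / 0.5 = 11.06; df 3 and 66; critical F 2.744; power 78.0%.

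**Neighbouring and planned sizes**

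| N | λ | df2 | Power |
|---|---|---|---|
| 24 | 11.06 | 66 | 78.0% |
| 25 | 11.52 | 69 | 79.9% |
| 26 | 11.98 | 72 | 81.7% |
| 28 | 12.90 | 78 | 84.9% |
| 30 | 13.82 | 84 | 87.6% |

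The first balanced total at or above 80% is 26.

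**Can another reading of the inputs give 24?**

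- *Unrounded f.* The quoted pulse wave velocities are 5.33 ± 0.46 and 5.15 ± 0.26 m/s. Then d = 0.18 / √((0.46² + 0.26²)/2) = 0.482 and f = d/2 = 0.2409. Power is 78.3% at 24 and 80.3% at 25, so the balanced answer is still 26.
- *Within-factor test.* With two groups it has the same degrees of freedom and gives 26. With one group it gives 25.
- *Between-factor test.* It gives 88.
- *The other two effect-size options.* Power at 24 is about 32% and 35%, so neither explains 24.
- *Epsilon below 1.* At 0.9, power at 24 falls to 74.6%.
- *What would give 24.* Power at 24 reaches 80% with f of about 0.2455 (ρ = 0.5) or ρ of about 0.522 (f = 0.24). With f = 0.25 it is 81.6%.

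**Power at the recruitment figures in the plan**

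- Section 17.1: 30 recruits, about 20% lost, 30 × 0.8 = 24 completers: 78.0%.
- Section 12.2 target: 30 completers: 87.6%.
- Section 12.2 cap with a full 20% loss: 36 × 0.8 = 28.8, so 28 completers: 84.9%.

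**The case against.** The strongest objection concerns consequence. A reader might infer that the trial is built around 24 completers, has no slack and misses its own stated power. The documents do not support that. Section 12.2 is the only place that gives an explicit completer target, and the target is 30. Section 17.1 never names 24 as the number expected to finish, and it gives reasons besides attrition for going to 30. The 78% figure therefore belongs only to Section 17.1's own recruitment step, read in isolation. This part of the objection stands in full.

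A second objection is that the gap is no larger than input rounding. The correlation is printed to one decimal, and 0.522 would print as 0.5. An f of 0.2449 would print as 0.24 and gives 79.8% at 24. This stands as a possible explanation, and it is why a misreported input is as plausible as a wrong total. It does not make the printed set reproducible, since the f derived from the quoted data is 0.2409 and still falls short at 24.

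A third objection is that Section 17.1 does not specify the calculation completely: the test, effect-size option and epsilon are not stated. That is correct, and 26 depends on the assumed settings. None of the alternatives tried at f = 0.24 and ρ = 0.5 returned exactly 24.

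Finally, replacing 24 with 26 could seem to accept the four-measure input. The analysis text in Section 17.1 frames the cf-PWV hypothesis as a comparison after two sleep conditions. With two measures and the same f and ρ, the total would be 38. That is a separate and larger question, which this point does not settle.

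**Conclusion.** The point holds as a minor error. On the printed inputs, 24 participants have 78.0% power and 26 are needed for 80%. The discrepancy is two participants and about two power points. Either the total is slightly wrong or an input was reported inexactly; the documents do not show which.

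The result assumes the within-between interaction test, the default effect-size option and epsilon 1. It takes f = 0.24 and four measures as given and endorses neither.

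It does not follow that the trial is underpowered on its own assumptions or that recruitment must rise. At the 30 completers sought in Section 12.2, power is about 88%; with 28 completers it is about 85%. The matter that needs settling alongside the figure is that Sections 12.2, 17.1 and 25.0 treat 30 as the number completing, recruited and required, respectively.

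**What to change.** Re-run the calculation and make one of three corrections in Section 17.1: state 26 (13 per group); keep 24 and give its power as 78%; or correct the input that was actually used. Name the G*Power test, the effect-size option and the epsilon so that the result can be reproduced.

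Then state the power at the number of completers the trial intends, and make Sections 12.2, 17.1 and 25.0 agree on whether 30 is the number recruited, completing or required.

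No increase in recruitment is needed. Even at 20% attrition, 26 completers need 26 / 0.8 = 32.5, so 33 recruits, or 34 for equal groups; both lie within the cap of 36 in Section 12.2. The cost is one corrected figure and a few sentences. The choice of four measures should be reviewed separately, and the calculation repeated if it changes.
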